7.2.1. Assessing Objective Tumor Response (RECIST v1.1)

- A comprehensive workup will be performed at baseline and every six weeks.
- Whenever the response criteria are met, the appropriate imaging tests will be repeated at least four weeks later in order to confirm the response.
- The same method will be used to evaluate each identified lesion both at baseline and throughout the study.
- Treatment will be administered as long as no disease progression or unacceptable toxicity is found, or as long as no other reasons for treatment discontinuation are met.
- Assessment of efficacy will be essentially based on a set of measurable lesions identified at baseline as target lesions and followed until disease progression and following the RECIST v1.1 criteria (Eisenhauer, 2009).

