8. STUDY ENDPOINTS

8.1. Primary endpoint

Phase I / Dose escalation part

Primary objective of the phase I trial is to establish the recommended phase II dose (RP2D), the maximum tolerated dose (MTD) evaluated on the first cycle (D1 to D21), the safety profile, and the Dose Limiting Toxicities (DLT) of trabectedin given in combination with durvalumab.

Definition:

Dose-limiting toxicity (DLT):

A DLT is defined as an AE or laboratory abnormality that fulfills all the criteria below:

- Begins on the first 21 days of treatment.
- Is considered to be at least possibly related to the study treatment.
- Meets one of the criteria below, graded as outlined or according to NCI-CTCAEv4.03 :
 - Any grade-4 toxicity (except for vomiting without maximal symptomatic/prophylactic treatment and if toxicity is transaminitis, but which have to be resolved at Day 21, i.e. return to Baseline or grade 1).
 - Grade-3 non-haematological toxicity lasting > 7days (except for 1rst episode of nausea without maximal symptomatic/ prophylactic treatment and if toxicity is transaminitis, which have to be resolved at Day 21, i.e. return to Baseline or grade 1).
 - Grade-3 hematologic toxicity lasting for > 7days.
 - Grade 4 neutropenia with fever.
 - Grade > 2 thrombocytopenia with bleeding.

Endpoints:

- Toxicity graded using the common toxicity criteria from the NCI-CTCAE v4.03.
- Incidence rate of DLT at each dose level during the first 21 days.

Phase I / Expansion cohorts

Primary objective of the expansion cohorts is to evaluate preliminary signs of the antitumor activity of trabectedin given in combination with durvalumab in terms of objective response under treatment. Following RECIST v1.1 recommendations ([appendix 3](#)):

- Objective response rate (ORR) is defined as the proportion of patients with complete or partial response (CR, PR) as per RECIST v1.1 criteria.
- Objective response under treatment is recorded from study treatment initiation until the end of treatment and determined once all the data for the patient is known.
- Claimed responses will have to be confirmed at least 4 weeks later to ensure responses identified are not the result of measurement errors.
- **Disease status under treatment, whatever the response observed, will be centrally reviewed for all patients, by an independent expert radiologist. Reviewed data will be used for the efficacy analysis.**

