9.1.1. Phase I (Expansion cohorts)

- The primary objective is to determine preliminary signs of anti-tumor activity of trabectedin given in combination with DURVALUMAB among two selected cohorts of patients (STS and ovarian carcinomas) in terms of objective response under treatment as per RECIST v1.1 criteria.
- Once the Maximum Tolerated Dose (MTD) is established for trabectedin, 2 distinct cohorts will be treated at the MTD:
 - Cohort A: patients with advanced STS.
 - Cohort B: patients with advanced ovarian carcinomas
- For each cohort:
 - Sample size is calculated based on the first stage of a 2-stage Gehan design assuming a 20% efficacy rate, 5% false positive rate and 10% precision (Gehan 1961).
 - 14 eligible and assessable subjects are required.
 - If at least one objective response (CR or PR as per RECIST v1.1) is observed under treatment, the study drug association will be considered worthy of further testing in this indication.

Assuming 10% patients not eligible or that cannot be assessed for the primary endpoint, **15 patients will be recruited for each of the 2 cohorts**, i.e. a total of **30 patients will be included in the expansion cohorts**.

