Complete or partial responses may be claimed only if the criteria for each are met at a subsequent time point as specified in the protocol (**generally 4 weeks later**). In this circumstance, the best overall response can be interpreted as in Table below.

Table 3 – Best overall response when confirmation of CR and PR required.

Overall response First time point	Overall response Subsequent time point	BEST overall response
CR	CR	CR
CR	PR	SD, PD or PR ^a
CR	SD	SD provided minimum criteria for SD duration met, otherwise, PD
CR	PD	SD provided minimum criteria for SD duration met, otherwise, PD
CR	NE	SD provided minimum criteria for SD duration met, otherwise NE
PR	CR	PR
PR	PR	PR
PR	SD	SD
PR	PD	SD provided minimum criteria for SD duration met, otherwise, PD
PR	NE	SD provided minimum criteria for SD duration met, otherwise NE
NE	NE	NE

CR = complete response, PR = partial response, SD = stable disease, PD = progressive disease, and NE = inevaluable.

a If a CR is truly met at first time point, then any disease seen at a subsequent time point, even disease meeting PR criteria relative to baseline, makes the disease PD at that point (since disease must have reappeared after CR). Best response would depend on whether minimum duration for SD was met. However, sometimes 'CR' may be claimed when subsequent scans suggest small lesions were likely still present and in fact the patient had PR, not CR at the first time point. Under these circumstances, the original CR should be changed to PR and the best response is PR.

Special notes on response assessment

When nodal disease is included in the sum of target lesions and the nodes decrease to 'normal' size (<10 mm), they may still have a measurement reported on scans. This measurement should be recorded even though the nodes are normal in order not to overstate progression should it be based on increase in size of the nodes. As noted earlier, this means that patients with CR (complete response) may not have a total sum of 'zero' on the case report form (CRF).

In trials where confirmation of response is required, repeated 'NE' time point assessments may complicate best response determination. The analysis plan for the trial must address how missing data/assessments will be addressed in determination of response and progression. For example, in most trials it is reasonable to consider a patient with time point responses of PR-NE-PR as a confirmed response.

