3.2.3 Primary endpoint

- Dose escalation part

Criteria	eFORM Variables	Control / program (TOL=1)
Toxicity will be graded using the common toxicity criteria from the NCI v4.0.	ADVERSE EVENT FORM AEVENT (adverse event) AESAE (is a serious adverse event) AE_NUMAE (Toxicity number) DT_SAE , DT_AE (date of beginning) DTENDAE (date of the end or death) INIT_INT, MAX_INT (intensity) TRAB_REL (relation to Trabectedin) DURV_REL (relation to Durvalumab) AE_TRA_MOD (Trabectedin modification) AE_DUR_MOD (Durvalumab modification) AE_OUTC (outcome)	Listing of Adverse events + descriptive statistics
Incidence rate of DLT will be reported at each dose level on cycle 1.	CYCLE 1 – TREATMENT DOSE_TRA DOSE-LIMITING TOXICITY FORM DT_EVENT OCC_CYC (occurred for the first 21 days) GR4_TOX GR3_NHT GR3_HT GR3_NEU GR2_THR OTH_DLT	Listing Of DLT + rate of DLT (Number of DLT / TOL) descriptive statistics

- Expansion cohorts

Criteria	eFORM Variables	Control (TOL=1)
Objective response rate, defined as the rate of complete or partial response according to RECIST v1.1	ASSE_CYC (TUMOR ASSESSMENT) DT_MEASC (date of measurement) ME1RTLC-ME5 RTLC (measures of lesions) SUM_RTLC (largest diameters) EVA1RLNMC-EVA5 RLNMC (non-measurable lesions eval) RES_RTLC, RES_RNTLC (target and non-target lesions) OV_REV (overall response) CR=1, PR=2, SD=3, PD=4, NE=5 New variables : NB_BORR (nb of objective response case) END OF STUDY (END_STU) DT_EOS (date of end of study)	Status at each TUMOR ASSESSMENT

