3.2.4 Secondary endpoints

For dose escalation part: Only the patients assessable for safety (TOL = 1) will take part into this analysis.

For expansion cohorts: Only the patients evaluable for efficacy (ELI_EFF = 1) will take part into this analysis.

Criteria	eFORM variable	Control
Objective response rate, defined as the rate of complete or partial response according to RECIST v1.1	
ASSE_CYC (TUMOR ASSESSMENT) DT_MEASC (date of measurement) ME1RTLC-ME5 RTLC (measures of lesions) SUM_RTLC (largest diameters) EVA1RLNMC-EVA5 RLNMC (non-measurable lesions eval) RES_RTLC, RES_RNTL (target and non-target lesions) OV_REV (overall response) CR=1, PR=2, SD=3, PD=4, NE=5 New variables : NB_BORR (nb of objective response case)
 
END OF STUDY (END_STU) DT_EOS (date of end of study)
	Status at each TUMOR ASSESSMENT
6-month objective response rate , defined as the rate of complete or partial response at 6 months according to RECIST v1.1	
ASSE_CYC (TUMOR ASSESSMENT) DT_MEASC (date of measurement) ME1RTLC-ME5 RTLC (measures of lesions) SUM_RTLC (largest diameters) EVA1RLNMC-EVA5 RLNMC (non-measurable lesions eval) RES_RTLC, RES_RNTL (target and non-target lesions) OV_REV (overall response) CR=1, PR=2 TREATMENT DT1_START ((Day 1 of treatment)) New variables : NB_ORR (nb of objective response case at 6months)
	DT_START filled in ME1RTLC-ME5 RTLC (filled in if needed) SUM_RTLC C filled in and check recist1.1 criteria EVA1RLNMC-EVA5 RLNMC (filled in if needed) RES_RTLC, RES_RNTL (filled in) Compute number of patients with OV_REV in (1 or 2) at 6 months
6-month Non-progression rate (NPR) defined as the percentage of patients with CR, PR or stable disease (SD) according to RECIST v1.1, (CR, PR or SD more than 24 weeks)	
ASSE_CYC (TUMOR ASSESSMENT) DT_MEASC (date of measurement) ME1RTLC-ME5 RTLC (measures of lesions) SUM_RTLC (largest diameters) EVA1RLNMC_EVA5RLNMC (non-
	DT_START filled in ME1RTLC-ME5 RTLC (filled in if needed) SUM_RTLC C filled in and check recist1.1 criteria EVA1RLNMC-EVA5 RLNMC (filled

	
measurable lesions eval) RES_RTL, RES_RNTL (target and non-target lesions) OV_RESP (overall response) CR=1, PR=2, SD=3 TREATMENT DT1_START ((Day 1 of treatment)) New variables : NB_NPR (nb of non-progression case at 6 months)
	
in if needed) RES_RTL, RES_RNTL (filled in) Compute number of patients with OV_REV in (1 2 3) at 6 month for at least 24 weeks

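### The SAP does not carry the protocol's 4-week response confirmation into its ORR derivations, so an unconfirmed CR or PR could be counted and could alone meet the go rule

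*SAP*

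**What the plan says.** **Protocol.** Section 8.1 makes objective response under treatment the primary endpoint of the expansion cohorts and adds: "Claimed responses will have to be confirmed at least 4 weeks later to ensure responses identified are not the result of measurement errors". Section 8.2 places the same condition in the ORR entry that covers both ORR under treatment and 6-month ORR, and the expansion cohorts take their secondary definitions from there. Section 7.2.1 provides the scan: once response criteria are met, "the appropriate imaging tests will be repeated at least four weeks later in order to confirm the response". Appendix 3 gives the classification rule: "Complete or partial responses may be claimed only if the criteria for each are met at a subsequent time point". It also assigns a task to the SAP: "The analysis plan for the trial must address how missing data/assessments will be addressed in determination of response and progression". Its example is the sequence PR-NE-PR.

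**SAP.** Section 3.2.3 defines the expansion primary endpoint as "Objective response rate, defined as the rate of complete or partial response according to RECIST v1.1". It lists the visit-level overall response OV_REV, the measurement dates and a counter NB_BORR. The control column says only "Status at each TUMOR ASSESSMENT". For the 6-month ORR, section 3.2.4 says: "Compute number of patients with OV_REV in (1 or 2) at 6 months". The SAP mentions confirmation of response only in its synopsis, under best overall response.

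**Go rule.** Protocol 9.1.1 and both synopses use the condition "If at least one objective response (CR or PR as per RECIST v1.1) is observed under treatment". If it is met, the combination is judged worth pursuing in that indication. The condition does not say that the response must be confirmed.

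**The concern.** This SAP is a programming specification. It spells out logic for eligibility, safety assessability, PFS and OS, and it states a duration condition where one is wanted (24 weeks for 6-month non-progression). A programmer working from 3.2.3 has dated visit statuses and a counter, but no instruction to look for a second scan, no minimum interval and no pointer to Appendix 3 Table 3. Section 3.2.4 has no derivation row for best overall response either, so no derivation in the SAP applies that table.

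A patient with one isolated PR could therefore be counted as a responder although Appendix 3 would classify the patient otherwise. The go rule needs only one responder per cohort, so one such patient could decide it. The ORR could also disagree with the best-response table for the same patients, if that table follows the synopsis and requires confirmation.

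**Working it through.** **1. The plan's own figure.** Inputs from Protocol 9.1.1: 20% efficacy rate, 5% error, go at one or more responses. The Gehan first stage takes the smallest n with (1 − 0.20)^n ≤ 0.05.

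- 0.8^13 = 0.0550
- 0.8^14 = 0.0440

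So n = 14, as stated. At a true rate of 20% the chance of a go is 1 − 0.0440 = 95.6%.

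**2. The same scan sequences under each document.**

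| Sequence | Protocol Appendix 3 | SAP 3.2.3 |
|---|---|---|
| PR then SD | SD | no rule |
| PR then PD | SD if the minimum SD duration is met, otherwise PD | no rule |
| PR then NE | SD if the minimum SD duration is met, otherwise NE | no rule |
| PR-NE-PR | reasonable to treat as confirmed; SAP to settle | no rule |
| PR, no later scan | not listed; nearest is PR then NE | no rule |

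Each sequence contains at least one visit with OV_REV = 2. The SAP's general statement that missing data are not imputed does not classify the last three.

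**3. Sensitivity of the go rule.** The documents give no rate of unconfirmed responses, so q is an assumption: the probability that a patient without a true response has at least one unconfirmed CR or PR reading. If nobody truly responds, P(at least one in 14) = 1 − (1 − q)^14.

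| q | P(go) if single readings count | P(go) if confirmation is required |
|---|---|---|
| 1% | 1 − 0.99^14 = 13.1% | 0% |
| 2% | 1 − 0.98^14 = 24.6% | 0% |
| 3% | 1 − 0.97^14 = 34.7% | 0% |
| 5% | 1 − 0.95^14 = 51.2% | 0% |

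At q = 5%, the chance that at least one of the two cohorts reaches a go is 1 − (1 − 0.512)^2 = 76.2%. Each counted unconfirmed response adds 1/14 = 7.1 percentage points to the ORR.

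**4. When some patients do respond.** Add an assumed 2% or 5% of patients with only an unconfirmed response to the true confirmed rate.

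| True confirmed ORR | P(go), confirmed only | plus 2% unconfirmed | plus 5% unconfirmed |
|---|---|---|---|
| 5% | 51.2% | 63.8% | 77.1% |
| 20% | 95.6% | 96.9% | 98.2% |

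The effect is large when the combination is inactive or weak, and small at the design rate of 20%.

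**5. Are the scans available?** Protocol 4.7 sets imaging every six weeks with a window of 7 days either way, and also asks for a scan at least four weeks after a first documented response. Two consecutive scheduled scans are at least 42 − 7 − 7 = 28 days apart, so the next scheduled scan can serve as confirmation.

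**The case against.** The strongest reply is that the confirmation rule is already in force. Protocol 8.1 presents confirmation as part of following RECIST v1.1, the SAP defines the ORR by RECIST v1.1, and nothing in the SAP sets 8.1 aside. SAP 3.2.2 assigns each patient a single response category, and dated visit statuses are exactly the input needed to apply confirmation. A go rule need not restate its endpoint's definition.

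Much of this stands. A reader might infer that the SAP deliberately counts a single reading for the primary ORR, or that the primary ORR as planned is inflated. The documents do not support either reading: 3.2.3 contains no counting rule at all, so the row is incomplete rather than contrary to the protocol.

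Two related items should not be pressed. The 6-month ORR does literally use one reading, but it is a secondary landmark that does not feed the go rule, and its formula matches Protocol 9.3.2.2. SAP Table 6.4, which reports responses at any evaluation in the first 6 months, describes timing in contrast to Table 6.2. It does not waive confirmation.

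It is also fair to say that q is assumed, that part of the sensitivity comes from the permissive rule itself (a true confirmed ORR of 5% also gives a go 51.2% of the time), that the analyses are descriptive, and that scans are read centrally by an independent expert. Central reading changes who reads the scan, not how many scans are required.

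What the reply does not cure is the missing step. The SAP's derivations omit a condition that the protocol attaches to this endpoint, and the SAP leaves undone the task that Appendix 3 assigns to it.

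**Conclusion.** The point holds as an omission. Protocol 8.1, 8.2 and Appendix 3 require confirmation; SAP 3.2.3 does not implement it for the primary ORR, and SAP 3.2.4 counts a single reading for the 6-month ORR. Programmed as written, the SAP could count an unconfirmed CR or PR as a response, and one such patient in 14 could alone meet the go rule.

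The 13% to 51% range rests on an assumed q of 1% to 5%, independence between patients and no true responders. It shows how sensitive the rule is and does not predict what the trial will see. The sample size of 14 is unaffected, provided the 20% target is read as a confirmed rate. Severity: should-fix, because the protocol's rule is clear and the repair is to the SAP's derivations and the go-rule wording.

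**What to change.** - **SAP 3.2.2 and 3.2.3.** Define a responder as a patient with centrally reviewed OV_REV of CR or PR at one assessment and again at an assessment at least 28 days later, before progression and before any new antitumour therapy. Apply Appendix 3 Table 3, with its footnote for CR followed by PR, to all other sequences. State that PR-NE-PR counts as confirmed and that a PR with no later scan does not count.
- **SAP 3.2.4, 6-month ORR.** Keep the landmark: count patients alive and in CR or PR at the 6-month assessment whose response is confirmed by another assessment at least 28 days apart. Using the primary definition here without the landmark would turn this endpoint into ORR under treatment.
- **Go rule.** In Protocol 9.1.1 and both synopses, specify a confirmed objective response on central review.
- **Reporting.** List unconfirmed responses separately.

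The cost is some SAP programming and a few words in the go rule. No new scans are needed, since Protocol 4.7 and 7.2.1 already require them. The downside is that the ORR may be slightly lower, because a response first seen on a patient's last scan will not count.

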3.2.4 Secondary endpoints

For dose escalation part: Only the patients assessable for safety (TOL = 1) will take part into this analysis.

For expansion cohorts: Only the patients evaluable for efficacy (ELI_EFF = 1) will take part into this analysis.

Criteria	eFORM variable	Control
Objective response rate, defined as the rate of complete or partial response according to RECIST v1.1	
ASSE_CYC (TUMOR ASSESSMENT) DT_MEASC (date of measurement) ME1RTLC-ME5 RTLC (measures of lesions) SUM_RTLC (largest diameters) EVA1RLNMC-EVA5 RLNMC (non-measurable lesions eval) RES_RTLC, RES_RNTL (target and non-target lesions) OV_REV (overall response) CR=1, PR=2, SD=3, PD=4, NE=5 New variables : NB_BORR (nb of objective response case)
 
END OF STUDY (END_STU) DT_EOS (date of end of study)
	Status at each TUMOR ASSESSMENT
6-month objective response rate , defined as the rate of complete or partial response at 6 months according to RECIST v1.1	
ASSE_CYC (TUMOR ASSESSMENT) DT_MEASC (date of measurement) ME1RTLC-ME5 RTLC (measures of lesions) SUM_RTLC (largest diameters) EVA1RLNMC-EVA5 RLNMC (non-measurable lesions eval) RES_RTLC, RES_RNTL (target and non-target lesions) OV_REV (overall response) CR=1, PR=2 TREATMENT DT1_START ((Day 1 of treatment)) New variables : NB_ORR (nb of objective response case at 6months)
	DT_START filled in ME1RTLC-ME5 RTLC (filled in if needed) SUM_RTLC C filled in and check recist1.1 criteria EVA1RLNMC-EVA5 RLNMC (filled in if needed) RES_RTLC, RES_RNTL (filled in) Compute number of patients with OV_REV in (1 or 2) at 6 months
6-month Non-progression rate (NPR) defined as the percentage of patients with CR, PR or stable disease (SD) according to RECIST v1.1, (CR, PR or SD more than 24 weeks)	
ASSE_CYC (TUMOR ASSESSMENT) DT_MEASC (date of measurement) ME1RTLC-ME5 RTLC (measures of lesions) SUM_RTLC (largest diameters) EVA1RLNMC_EVA5RLNMC (non-
	DT_START filled in ME1RTLC-ME5 RTLC (filled in if needed) SUM_RTLC C filled in and check recist1.1 criteria EVA1RLNMC-EVA5 RLNMC (filled

	
measurable lesions eval) RES_RTL, RES_RNTL (target and non-target lesions) OV_RESP (overall response) CR=1, PR=2, SD=3 TREATMENT DT1_START ((Day 1 of treatment)) New variables : NB_NPR (nb of non-progression case at 6 months)
	
in if needed) RES_RTL, RES_RNTL (filled in) Compute number of patients with OV_REV in (1 2 3) at 6 month for at least 24 weeks

1 and 2-year Progression-Free Survival (PFS) defined as the time from study treatment initiation to the first occurrence of disease progression or death (of any cause), whichever occurs first.	
END OF TREATMENT FORM DT_SOT (Date of start of treatment) EOTSTATU (Status) EOTREAO (Reason end) DT_PROG (Date of progression if occurred) Type of progression (if progression occurred) FOLLOW UP FORM DT_FUP (date of visit) STATUSP (Vital status) PRO_LAS, DT_FPROG (date of progression) END OF STUDY (END_STU) DT_EOS (date of end of study) REA_STUD (reason) DT_DEATH (date of death)
	
Check if everything is filled in If (DT_PROG is blank) then Do; If (PRO_LAS=0) then { PFS= DT_EOS-DT_SOT ; If (REA_STUD='death') then IND_PFS=1 Else IND_PFS=0 } Else { PFS=DT_FPROG – DT_SOT; IND_PFS=1} End; Else { PFS= DT_PROG – DT_SOT; IND_PFS=1}

1 year Overall Survival (OS), OS is defined as the time from study treatment initiation to death (of any cause).	
END OF TREATMENT (EOTF) DT_SOT (start date of treatment) EOTSTAU (Status) EOTREAO (Reason end) FOLLOW UP FORM DT_FUP (date of visit) STATUSP (Vital status) END OF STUDY (END_STU) DT_EOS (date of end of study) REA_STUD (reason) DT_DEATH (date of death) DT_LFUP (date of last follow_up)
	
Check if everything is filled in If (STATUSP NE 'dead') then do; if (REA_STUD ='death') then { OS= DT_DEATH-DT_SOT; IND_OS=1; } Else {OS= DT_EOS-DT_SOT; IND_OS=0; } end; Else { OS= DT_LFUP -DT_SOT; IND_OS=1; }

Pharmacodynamic (PD) and predictive biomarkers analysis (levels of angiogenic and immunologic biomarkers in blood at baseline and different study time points).	
LABORATORY TEST BIOMARKERS AND CIRCULATING DNA
	

4 Annexes

